To Determine DHCW and Patient Willingness/Ability to Follow Thru with Triage, Testing and Survey Administration Procedures	Determining willingness and ability to follow thru with triage, testing and survey administration procedures is important for refining the survey procedures	
For both DHCW and Patients
 
 % who complete the study % who complete surveys 
 Start-of-Study DHCW Survey End-Of-Study DHCW Survey Pre-Visit Patient Survey End-of-Visit Patient Survey % activities occurring within the defined window 
 Consents Start-of-Study DHCW Survey, Triage and Testing End-Of-Study DHCW Survey, Triage and Testing Mid-Study Triage Testing Pre-Visit Patient Survey End-of-Visit Patient Survey Patient Testing % who feel testing (Saliva, PCR, POC, and ELISA Antibody) procedure was easy to comply with 
 Specimen collection Specimen preparation for shipping Specimen storage Timeliness of results Reporting of results 	
% Complete Study:
 
 For DHCW - At time End-of-Study (Day 28) Patients – End-Of-Visit (Day 1) 
% All Surveys Completed:
 
 For DHCW - At time End-of-Study (Day 28) Patients – End-Of-Visit (Day 1) 
% Activities Occurring within the defined window:
 
 For DHCW – Consent, Start-of-Study Visit, Mid-Visit, End-of-Study Visit Patients – Consent, LAB material receipt, LAB specimen sent to laboratory, LAB results, Treatment Visit 
% Feel Testing Protocol was Easy to Comply With:
 
 For DHCW - At time End-of-Study (Day 28) Patients – End-Of-Visit (Day 1)

Objectives	Brief Description/Justification of Outcome Measure	Outcome Measured By	Time Frame

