 - Complete COVID-19 POC test** (administered by PBRN practitioner or designated investigator)
 - A nasal swab will be swept inside the participant's nose (not beyond the nares) to collect the specimen for the COVID-19 test
 - The PBRN Practitioner or their designee will process the specimen
- At the End of the Dental Visit
 - Complete two electronic surveys
 - *Patient End-of-Visit Survey*
 - Questions explore perceptions with testing preferences, PPE observed, environmental controls observed, concerns about returning to dental care, safety precautions valued, importance of triage and testing, likelihood of reporting symptoms, dentist's role in COVID-19 testing and vaccinations
 - *Patient Participation Survey*
 - Questions explore perceptions related to study participation including survey and testing logistics

*If any aspect of the COVID-19 triage screening is positive without any preexisting condition which could explain the positive screening (i.e.. a history of hay-fever which likely explains sneezing or a report of physical activity which likely explains muscle soreness), appointment will be postponed, and the participant will be referred to their primary care physician for further testing.

- A Positive screening by reporting one or more symptoms of unknown origin
- A positive temperature is considered greater than 100.4 degrees F
- A positive pulse oximeter is considered when the blood oxygen saturation level is below 95%

**If the POC COVID-19 test is positive, the dental visit may be postponed, and the positive patient participant will be instructed to consult with their primary care provider for further testing.

Group 3- DHCWs in LAB Offices

Consent Process for Group 3- DHCWs in LAB Offices

Within 4 weeks prior to study initiation in the dental office, the National Dental PBRN Node Coordinator will consent the DHCWs in the participating office. The consent will clearly outline participant expectations and offer the opportunity for potential participants to contact the National Dental PBRN Node Coordinator for more information as needed. DHCWs who elect to participate will affirm their willingness to participate by signing the consent form.

Study Procedures for Group 3- DHCW in LAB Offices

Prior to study initiation (Up to 4 weeks prior)

- Complete consent for all DHCW participants

Day 1

- Complete an electronic survey: *DHCW Start of Study Survey*

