 - Questions explore perceptions of safety and comfort, reasons for delaying dental care, concerns about returning to dental care, safety precautions valued, importance of triage and testing, and demographics
 - Launched automatically after the completed consent
 - Receive a saliva collection kit by mail
- One week before the dental visit
 - Complete a COVID-19 saliva test
 - Spit into a tube
 - Package as directed
 - Drop off the completed test kit at a UPS Store or drop-off box
- At the start of the Dental Visit
 - Undergo a COVID-19 triage screening in the office*
 - Screening includes symptom questions, temperature check, and pulse oximeter reading
- At the End of the Dental Visit
 - Complete two electronic surveys
 - Patient End-of-Visit Survey*

- Questions explore perceptions with testing preferences, PPE observed, environmental controls observed, concerns about returning to dental care, safety precautions valued, importance of triage and testing, likelihood of reporting symptoms, dentist's role in COVID-19 testing and vaccinations
- *Patient Participation Survey*
 - Questions explore perceptions related to study participation including survey and testing logistics

*If any aspect of the COVID-19 triage screening is positive without any preexisting condition which could explain the positive screening (i.e., a history of hay-fever which likely explains sneezing or a report of physical activity which likely explains muscle soreness), the appointment will be postponed, and the participant will be referred to their primary care physician for further testing.

- A Positive screening by reporting one or more symptoms of unknown origin
- A positive temperature is considered greater than 100.4 degrees F
- A positive pulse oximeter is considered when the blood oxygen saturation level is below 95%

**If the lab processed SARS-CoV-2 test is positive, the dental visit may be postponed, and the positive patient participant will be instructed to consult with their primary care provider for further testing.

Reporting and Notification

The results of the POC, LAB, and/ Elisa test will be recorded in the *Testing Case Report* form in REDCap. The PI and/or Chief Protocol Officer will notify the Practitioner of test results. The National Dental PBRN dentist member of the practice will be considered the "Practitioner" of the office and assume the responsibility of notifying test results to the DHCWs and patients in the practice.

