For the purpose of this study, a COVID-19 positive result is not considered an adverse event though results of this test will be recorded.

DHCW subjects who test antigen or viral positive or who triage positive without any preexisting medical condition will be instructed to speak to their physicians for a definitive diagnosis and follow-up. If a DHCW is back to work in time for the mid-study testing, the mid-study protocol will be followed. Similarly, if a DHCW can return to work in time for the end-of-study testing, the end-of-study protocol will be followed. In either case, a follow-up call by the PBRN practitioner or designated investigator will be made approximately 1 week after the positive triage finding or test result to record any confirmatory tests which were obtained based upon the advice of the DHCW's physician.

Patient subjects who are COVID-19 antigen or viral positive or who triage positive without any preexisting medical condition, will not be seen for their scheduled dental visit. The subject will be referred to their physician for a definitive diagnosis and follow-up.

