Patient Start-of-Visit Survey • Safety and Comfort • COVID-19 Testing Preferences • Perception of Importance • Medical history Likelihood to report COVID-19 symptoms	Collect outcome measures	Yes	2 Weeks Prior (day-14 +/- 7 days)	Data entered via REDCap self-administered survey.
Triage Case Report	Collect COVID-19 screening data	Yes	Visit (day 1)	Data entered into REDCap by the PI and/or Chief Clinical Officer
Testing Case Reports	Collect information on outcomes of COVID-19 testing		Day Prior (day -2 +/- 2 days)	Saliva Viral SARS-CoV-2 test results entered into REDCap via eCRF by the Practitioner or their investigator designee
Dental Procedures Performed	Maintain patient oral health	NO	Visit	Completed by Dental Health Care Workers
Patient End-of-Visit Survey • PPE observed in office • Environmental controls observed in office	Collect outcome measures	Yes	Visit (day 1)	Data entered via REDCap self-administered survey.
Patient Participation Questionnaire	Collect feasibility information on surveys and logistics	Yes	End of Study (Day 28)	Data entered via REDCap self-administered survey.

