Tracking of Specimen Collection Kits	Not applicable (POC Test)	REDCap System and/or Excel Worksheet	REDCap System and/or Excel Worksheet
Tracking of Tests Administered	Completion of REDCap SARS-CoV-2 Test Order and Results Form (which enables the generation of a Specimen Tracking Log)	Completion of REDCap SARS-CoV-2 Test Order and Results Form (which enables the generation of a Specimen Tracking Log)	Completion of REDCap SARS-CoV-2 Test Order and Results Form (which enables the generation of a Specimen Tracking Log)
Results			
Processing Time	15 minutes	Results are available within 1 week.	Results are available within 1 week
Recording Results in REDCap	Via posting in REDCap by PBRN Practitioner or designated investigator	Via secure e-mail and web site and then posted into REDCap by the Rutgers research staff	Via secure e-mail and then posted into REDCap by the Rutgers research staff
Notifying participants	National Dental PBRN Practitioner or designated investigator	PBRN Practitioner results- by the PI and/or Clinical Chief DHCW and Patient results- by the National Dental PBRN Practitioner or designated investigator	PBRN Practitioner results- by the PI and/or Clinical Chief DHCW and Patient results- by the National Dental PBRN Practitioner or designated investigator
Reporting to State Department of Health	PI, Chief Clinical Officer, PBRN Practitioner or designated investigator	Genomics Laboratory	Not Applicable

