7.2.3 Specimen Shipment

Saliva for LAB, and nasal swab for the PCR Viral Test specimens are collected and immediately placed into a preservative. The Mitra Cartridge includes a desiccant or sample preservation. All can be stored at room temperature for at least one week.

	POC Test	PCR Viral Test	ELISA Antibody Test
Shipment Method and Frequency	Not applicable	Samples will be obtained from subjects Monday and Wednesday and sent to the Rutgers School of Dental Medicine via UPS or Federal Express.	Specimens will be mailed via UPS or Federal Express.
Packaging Specimen for Shipping	Not applicable (POC Test)	Specimens are placed into biohazard plastic bag, sealed then placed into a 95 kPa biohazard bag with absorbent, sealed and then placed into a UN3373 Category B certified box.	Post sampling, the closed Mitra Cartridge is inserted into sealed specimen bag which contains a desiccant that absorbs moisture then placed into a 95 kPa biohazard bag with absorbent and inserted in a shipping UN3373 Category B certified box.
Shipping Address	Not applicable	Rutgers University School of Dental Medicine [name] Newark, NJ 07103	Rutgers University School of Dental Medicine [name] Newark, NJ 07103
Contact Information for Laboratory Personnel	Not applicable	[name] [contact] [contact] [name] [contact] [contact]	[name] [contact] [contact]
Days and Times shipments are allowed	Not applicable	Monday thru Friday 9:00 am to 5:00 pm	Monday thru Thursday 9:00 am to 5:00 pm
Labeling Requirements for Specimen Shipping	Not applicable	Subject Number, Subject Name, and Collection Tube ID/Bar Code	Subject Number, Subject Name and Mitra Cartridge ID/Bar Code
Special Instruction for Specimen Collection	No special instructions	Subject should not eat or drink for 30 minutes prior to saliva and tongue cell specimen collection	Clean area for finger prick with alcohol gauze prior to pricking finger
Special Instructions for Specimens for Shipment (i.e., dry ice, wet ice)	Not applicable	No special instructions	No special instructions
Completion of Specimen-Tracking Log	Completion of REDCap COVID-19 Test Order and Results Form (which enables the generation of a Specimen Tracking Log)	Completion of REDCap COVID-19 Test Order and Results Form (which enables the generation of a Specimen Tracking Log)	Completion of REDCap COVID-19 Test Order and Results Form (which enables the generation of a Specimen Tracking Log)

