15.6 Protocol Deviations

A protocol deviation is any change, divergence, or departure from the study design or procedures of a research protocol that is under the investigator's control and that has not been approved by the sIRB. Since the purpose of this feasibility study is for protocol refinement, any of the following will not be considered protocol violations unless the subject was put at additional risk as a result of the divergence from the protocol.

- Incomplete visits
- Activities occurring outside of the specified windows
- Missing surveys/forms or data

Upon discovery of a protocol deviation, the Principal Investigator is responsible for reporting protocol deviations to the sIRB.

A protocol violation is a deviation from the sIRB approved protocol that may affect the subject's rights, safety, or well-being and/or the completeness, accuracy and reliability of the study data. Protocol Violations must be submitted for Full Board sIRB review. If the deviation meets any of the following criteria, it is considered a protocol violation.

All deviations and violations from the protocol will be recorded on the Protocol Deviation/Violation Reporting Form no later than 10 business days after study staff become aware of the deviation and

forwarded to the study PI for review and reported promptly to the sIRB. All protocol deviations and violations will be reviewed monthly during the PREDICT Steering Committee Meeting.

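### The permitted LAB-patient timings allow a saliva result to arrive on or after the dental visit, and the planned in-window percentage may not show how often that happens

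*Combined protocol and SAP*

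**What the plan says.** Four entries fix the timing for patients in LAB offices.

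- Section 6.2 (LAB schedule) puts the saliva specimen at Day -7 with a margin of 5 days either way, and the visit on Day 1.
- Section 7.2.2 says of the PCR test: "Results are available within 1 week". It does not say whether the week starts at collection, drop-off or laboratory receipt.
- Section 7.1 (Group 4 table) dates the Testing Case Report, in which the saliva result is recorded, as "Day Prior (day -2 +/- 2 days".
- Section 15.2 has PCR results entered into REDCap when the laboratory's e-mail arrives.

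On acting on a positive, Reporting and Notification in Section 7 says: "Patient subjects who are COVID-19 antigen or viral positive or who triage positive without any preexisting medical condition, will not be seen" for the planned visit. The Group 4 footnote in the same section says: "If the lab processed SARS-CoV-2 test is positive, the dental visit may be postponed". The Group 2 footnote says: "If the POC COVID-19 test is positive, the dental visit may be postponed". None of these covers a result that is still pending on the day.

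The nearest planned measure is in Section 3.0, the percentage of activities within their windows. For patients it lists consent and then "LAB material receipt, LAB specimen sent to laboratory, LAB results, Treatment Visit". Section 11.1 plans frequencies of each variable.

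**The concern.** In the LAB arm, testing before the visit is useful only if the office has the answer before the patient is in the chair. If the permitted collection window and turnaround let a result arrive later, the bar on seeing a viral-positive patient cannot operate for that patient, although everyone has followed the plan. When the result is in hand, the office has two instructions for a positive, one mandatory and one discretionary.

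The second issue is measurement. Section 8.1.3 gives testing the study windows as the purpose of the pilot, and Section 2.1 names slow results as one obstacle to routine testing. A larger study would want to know how often the LAB result reached the office in time. A percentage that treats a very early result and a post-treatment result alike does not answer that.

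**Working it through.** **Inputs.** Collection day c runs from -7 - 5 = -12 to -7 + 5 = -2, which is 11 permitted days (Section 6.2). Turnaround T is at most 7 days (Section 7.2.2). The result-entry window runs from -2 - 2 = Day -4 to -2 + 2 = Day 0 (Section 7.1). The visit is Day 1. Because the entry window reaches Day 0, I take Day 0 as the day before the visit.

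**Formula.** Result day = c + T, with the clock starting at collection. A result is in time if c + T ≤ 0.

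**Nominal schedule.** c = -7 and T = 7 give Day 0, which is in time and inside the entry window. The central schedule therefore fits on this clock.

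**Whole permitted window.** Number of the 11 collection days falling in each class:

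| T (days) | Before Day -4 | Day -4 to 0 | Day 1 or later |
|---|---|---|---|
| 2 | 6 | 5 | 0 |
| 3 | 5 | 5 | 1 |
| 4 | 4 | 5 | 2 |
| 5 | 3 | 5 | 3 |
| 6 | 2 | 5 | 4 |
| 7 | 1 | 5 | 5 |

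At T = 7 the five late days are c = -6 to -2, with results on Day 1 to Day 5.

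**Clock starting at laboratory receipt.** The documents give no transit time, so I assume 1, 2 or 3 days. Result day = c + transit + 7. The late days become 6, 7 or 8 of 11, and a nominal Day -7 specimen can report on Day 1, 2 or 3.

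**Sampling days.** Section 7.2.3 says of PCR specimens: "Samples will be obtained from subjects Monday and Wednesday". If that covers LAB patients, a Monday-to-Friday visit has 3 + 3 + 2 + 3 + 3 = 14 permitted pairs of visit weekday and collection day. With the clock at collection, T = 7 gives 2 + 1 + 1 + 1 + 1 = 6 of 14 late, T = 5 gives 3 of 14, and T = 2 gives none.

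**What the in-window percentage shows.** Two assumptions are needed: that Section 3.0 scores LAB results against the Day -4 to Day 0 window, and that results are entered on receipt, as Section 15.2 indicates. A Day -7 specimen with T = 1 or 2 then reports on Day -6 or -5, which is out of window although in time. A specimen reporting on Day 1 or later is also out of window. With T of at least 1 day, the early class can arise only for c = -12 to -6. For c = -5 to -2, being in window and being in time are the same thing.

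A hypothetical case shows the effect. There are at most 2 offices x 20 = 40 LAB patients. If 10 results are early and 30 in window, the measure is 30/40 = 75%, and 40/40 had a result before the visit. If 10 are late and 30 in window, the measure is again 75%, but only 30/40 had one.

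**The case against.** The strongest reply is that the schedule is coherent and only its edge is loose. The nominal Day -7 specimen fits, a week is an upper limit, and Section 7.2.2 gives about four hours for PCR processing itself. This stands. A reader might infer that the three timings contradict each other outright, and the documents do not support that: a late specimen and a slow result must coincide, or the clock must start after collection.

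A second reply is that the Section 7.1 window is for completing a form, so an early result could be held and entered on Day -4, and that Section 3.0 does not name this window. The latter is correct, so the measurement point is conditional. The holding argument is weak, because Section 15.2 has results entered when the e-mail arrives, and Day -4 to Day 0 is the only dated window given for the LAB patient result.

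A third reply is that nothing is lost: scoring the window already needs a result date, so patients treated with a result pending could be counted later. That also stands. However, no planned measure asks for the count. Section 11.1 has a three-point timeliness rating and a yes/no completeness item for the Testing Case Report, neither of which carries a date. Section 3.2 counts patients unable to attend, not those seen without a result.

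A fourth reply is that patients are protected anyway. Dental treatment lies outside the research protocol, triage is done at the visit, and each office's infection control applies (Section 2.2.1). Missed windows "will not be considered protocol violations unless the subject was put at additional risk as a result of the divergence from the protocol" (Section 15.6), so an added-risk case can still be reported. These points limit the harm but do not supply the missing instruction.

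**Conclusion.** The point holds in a limited form. As written, the plan allows a LAB patient's result to arrive on or after the visit, in which case the rule against seeing a viral-positive patient cannot be applied. The two wordings for a known positive also conflict. With the clock at collection, the exposure is 5 of 11 permitted collection days at a full week and none at two days. It is larger if the week starts at laboratory receipt. The claim that the planned percentage cannot separate early from late results rests on the two scoring assumptions stated with the calculation.

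A reader might take 5 of 11 as the share of patients affected. It is not: it counts calendar days, and the documents give neither the spread of collection days nor the actual turnaround. A reader might also infer that late results would go unseen. On the same scoring they would lower the percentage, but mixed with early ones. The number affected is unknown, at most 40 patients are concerned, and other safeguards remain. Severity is low.

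**What to change.** 1. In Sections 3.0 and 11.1, report the percentage of LAB patients with a result posted before the visit and the number treated with a result pending. Do not score an early result as out of window. Once any result posted by Day 0 counts as in window, the in-window percentage and the first of these figures are essentially the same, so one line can serve for both.
2. In the Group 2 and Group 4 footnotes of Section 7, replace the optional postponement with the mandatory rule in Reporting and Notification.
3. In Section 7.2.2, state when the one-week clock starts. Record a pending result for any patient who has none on Day 1. Whether to hold such a visit is for the sponsor to decide, since holding delays care and treating accepts some risk.

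Leave the collection window as it is. Ending it at Day -7 would make every specimen at least 1 - (-7) = 8 days old at the visit, and would narrow a window that the pilot is meant to test.

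The cost is a minor wording amendment with sIRB approval (Section 14.2), one proportion and one count from dates already needed, and no new visit or specimen. LAB testing may look less feasible once late results are shown separately.

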The PRBN Node Research Coordinator will recruit PBRN dentist members to participate in the protocol. The PBRN Node Research Coordinator will contact PBRN dentist members to introduce the study and gauge initial interest. The dental office will be enlisted if the PBRN dentist member and 4-9 additional office DHCWs of the practice are willing to participate and the PBRN member is willing to perform the responsibilities of the protocol including enrolling and completing 10 patients. The PBRN practitioner's preference will determine which protocol (POC or LAB) will be followed in the office. In total, two POC offices will participate, and two LAB offices will participate.

Office	Study Group	Protocol	COVID-19 Related Tests (Method)
POC	1- DHCW in POC Offices	POC DHCW Protocol	
• Antigen (nasal swab)• Antibody (capillary blood)
	2- Patients in POC Offices	POC Patient Protocol	
• Antigen (nasal swab)
LAB	3- DHCW in Lab Offices	LAB DHCW Protocol	
• Virus (saliva and/or tongue)• Antibody (capillary blood)
	4- Patients in LAB Offices	LAB Patient Protocol	
• Virus (saliva)

Retention: In order to minimize loss of study participants and/or incomplete data collection, the following activities will take place:

- Node Coordinators will work with National Dental PBRN study participants responsible for recruiting subjects and completing surveys to encourage patient enrollment and study completion.
- Participants will receive compensation.

Compensation and Scheduled Payments: DHCWs who complete the study procedures including the end-of-study survey will receive \$125 each. Patients who complete the LAB study procedures including the post-visit survey will be provided \$100 and patients who complete the POC study procedures including the post-visit survey will be provided \$50.

Additional Plans to Minimize Missing or Incomplete Data: The following will minimize missing or incomplete data:

- When appropriate, REDCap survey data fields are set to "required".
- REDCap validation rules on data fields to limit responses to those which are valid

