6.3 Unscheduled Visit

Not applicable. For dental patient participants, the study takes place during 1 patient dental visit. For Dental Healthcare Workers, data collection occurs at three specific times over a one-month period: start, mid-month, end of month.

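### Patients deferred for a positive test or unexplained positive triage have no clear route to the closing surveys, so testing percentages can omit them and completion mixes deferral with unwillingness (minor)

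*Combined protocol and SAP*

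**What the plan says.** Section 7 (Reporting and Notification) says that patients who are antigen or viral positive, or who triage positive "without any preexisting medical condition, will not be seen for their scheduled dental visit". They are referred to a physician, and no further study step is stated. Dental health care workers (DHCWs) do have a return rule in the same section: "Similarly, if a DHCW can return to work in time for the end-of-study testing, the end-of-study protocol will be followed". They also have a parallel mid-study rule and a follow-up call after about one week.

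The patient schedule in Section 6.2 and the Group 2 and Group 4 procedures in Section 7 place both closing instruments, the End-of-Visit Survey and the Participation Questionnaire, at the end of the Day 1 visit. Section 6.3 adds: "For dental patient participants, the study takes place during 1 patient dental visit". The Section 7.1 tables for the same two groups instead place the Participation Questionnaire at Day 28.

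Section 3.0 measures the percentage "who complete the study" and the percentage "who feel testing (Saliva, PCR, POC, and ELISA Antibody) procedure was easy to comply with". The second includes timeliness and reporting of results. For patients, both are timed at the end of the Day 1 visit. On payment, Section 5.3 says "Patients who complete the LAB study procedures including the post-visit survey will be provided" a sum of $100. The point-of-care group is paid $50 on the same condition.

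After a positive test, the Group 2 and Group 4 footnotes in Section 7 allow the visit to be postponed but do not require it. After an unexplained positive triage they do require postponement.

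**The concern.** A patient who is turned away under the protocol's own rule does not reach the point at which the closing instruments are given. Two feasibility outcomes are touched.

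- **Testing logistics.** The percentages for ease, timeliness and reporting would come only from patients who were treated. Patients with a positive result are well placed to say whether it reached them in time, and they would be missing.
- **Completion.** Section 4 names completion of the protocol as an important outcome, and Section 11.1 plans frequencies without a denominator rule. A patient who did everything asked and was then deferred could be counted with those who declined or were lost. Section 13 treats incomplete surveys as an outcome and does not chase them, and Sections 8.1.3 and 15.6 do not count them as deviations, so nothing else would show the difference.

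The disagreement about postponement is a separate matter. It leaves an office with two different instructions on infection control after a positive test.

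**Working it through.** **Texts side by side**

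| Item | One place | Another place |
|---|---|---|
| Visit after a positive test | Section 7, Group 2 and 4 footnotes: postponement optional | Section 7, Reporting and Notification: patient not seen |
| Visit after unexplained positive triage | Footnotes: postponed | Reporting and Notification: not seen (agrees) |
| Participation Questionnaire, patients | Section 6.2 and Section 7 lists: Day 1 | Section 7.1 tables: Day 28 |
| Where patients enter surveys | Section 15.2 table: at home, own device | Section 15.2 text: study-provided pads for all but consent and pre-visit survey |
| Return to study after a positive finding | DHCWs: stated | Patients: not stated |

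Day 28 fits poorly with the Day 1 time frame in Section 3.0 and with patient participation of about two weeks (Protocol Summary, Section 4). It may be an entry carried over from the DHCW tables, but that is a guess.

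**Timing of LAB results.** Section 6.2 sets specimen collection at Day -7 +/- 5, so as late as Day -2. Section 7.2.2 gives results within 1 week. Day -2 plus 7 days is Day 5, after the Day 1 visit. A rule that always postpones after a positive LAB result could not be followed in that case.

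**Size.** The plan states no figure to reproduce; Section 11 says that no sample size calculation was done. Inputs from the plan are at most 20 patients in each of 4 offices, with 2 offices per testing protocol, giving 80 patients in total and 40 per protocol. Two inputs are assumptions: a deferral fraction d of 2% to 10% (test or triage), and p = 90% of responders calling testing easy.

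- Expected deferrals: 80d and 40d.
- Chance of at least one deferral among 80, if independent: 1 - (1 - d)^80.
- Highest possible completion if deferred patients count as non-completers: 1 - d.
- Range for the all-patient percentage if no deferred patient answers: p(1 - d) to p(1 - d) + d.
- Worst-case shift: p × d.
- 95% half-width among responders: 1.96 × √(0.09 / (n(1 - d))).

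| | d = 2% | d = 5% | d = 10% |
|---|---|---|---|
| Deferred of 80 (of 40) | 1.6 (0.8) | 4 (2) | 8 (4) |
| Chance of at least one of 80 | 80% | 98% | >99% |
| Highest completion | 98% | 95% | 90% |
| All-patient range | 88.2–90.2% | 85.5–90.5% | 81–91% |
| Worst-case shift (points) | 1.8 | 4.5 | 9.0 |
| Half-width, n = 40 (points) | 9.4 | 9.5 | 9.8 |
| Half-width, n = 80 (points) | 6.6 | 6.7 | 6.9 |

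The shift equals the half-width at d = 10.9% for n = 40 and at d = 7.6% for n = 80.

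**Payment.** Full completion costs 40 × $100 + 40 × $50 = $6,000. The share tied to deferred patients is 40d × $100 + 40d × $50 = $6,000d, or $120 to $600. The ceiling, if all 8 were LAB patients, is 8 × $100 = $800.

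**The case against.** **A route may exist.** Read literally, the Day 28 entries in Section 7.1 give deferred patients access to the Participation Questionnaire, which covers testing logistics. A postponed appointment implies a later one, and Section 15.6 tolerates late or incomplete activities unless they add risk. This stands in part. A reader might infer that deferred patients can never finish the study, and the documents do not support that. They contain one conflicting route and leave the rest unstated. Tolerating a late activity does not say that study procedures move to the later appointment.

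**Some missing data are inherent.** The End-of-Visit Survey asks about protective equipment and environmental controls observed. An untreated patient cannot fully answer those items. This stands, and it limits what should be sent on deferral.

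**The numbers are small and loosely matched to the harm.** The assumed rate covers triage deferrals, who may have no positive result. Point-of-care results take 15 minutes, so timeliness is mainly a LAB question, and the number of LAB test-positives is not estimated here. With the minimum of 10 patients per office in Section 5.3, n = 20 per protocol and the half-width is about 13 to 14 points, before any allowance for clustering by office. Pooling the two protocols is of limited relevance, because Section 11.1 lists logistics test by test. No go/no-go threshold is set. All of this stands. A reader might infer a material bias in the feasibility results, and the documents do not support that either.

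**Payment.** A reader might infer that patients would hide symptoms to keep $50 or $100. Section 2.2 speaks of fear of not being seen, not of losing money, and the consent pages, which may carry a payment rule, are not in the reviewed text. The incentive is conjecture. What stands is that Section 5.3 has no rule for deferred patients.

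**Deferral is already visible.** Triage and testing case reports identify these patients, and Section 3.2 counts patients unable to attend. That makes separate reporting easy, but Section 3.2 lists outcomes for the full study and does not define the completion percentage in Section 3.0.

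**Conclusion.** The point holds at minor severity. Followed as written on the Day 1 reading, the plan leaves deferred patients out of the testing-logistics percentages and does not separate deferral from unwillingness in the completion percentage. The two wording conflicts, on postponement after a positive test and on the questionnaire date, can be confirmed from the text without any assumption. The size rests on the assumed 2% to 10% deferral and 90% ease. Under these, the worst-case shift is 1.8 to 9.0 points, below sampling error within one protocol throughout, and above it for pooled patients only when deferral exceeds 7.6%. The direction cannot be known in advance. The case for acting is a missing rule and contradictory instructions in a study meant to refine procedures.

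**What to change.** 1. On deferral, send the Participation Questionnaire and the testing items of the End-of-Visit Survey by REDCap link, leaving out items on equipment and environmental controls that the patient could not observe. Align the table and text of Section 15.2 accordingly.
2. In Section 3.0 or 11.1, report completion among all enrolled patients, with those deferred per protocol on a separate line from those who declined or were lost, using the triage and testing case reports.
3. In the Group 2 and Group 4 footnotes of Section 7, say that the visit will be postponed if the positive result is known before treatment. Qualify Reporting and Notification in the same way for LAB results that arrive after the visit.
4. In the Section 7.1 tables for Groups 2 and 4, set the Participation Questionnaire to Day 1, or to the time of deferral.
5. Unless the consent form already says so, state in Section 5.3 that deferred patients who complete the steps open to them are paid.

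The cost is one REDCap link, short text edits, and about $120 to $600 in payments under the assumed rates (at most $800). Those payments fall within the $6,000 that full completion by 80 patients would cost anyway. Patients must already have an internet-connected computer or tablet to enrol (Section 5.1), so the link needs no new equipment.
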